5.3.6 Other Considerations

There are no other specific considerations that are not covered in other sections of this SAP.

5.4 Efficacy Analyses

Tumor response will be assessed using RECIST 1.1 criteria ([Eisenhauer, 2009](#)). For this study, a confirmation of CR or PR is required by a consecutive tumor assessment no less than 4 weeks after the initial assessment of response.

The primary efficacy analyses will be based on the investigator assessments. The stratification factors (ie, MSKCC prognostic group and prior PD-1/PD-L1 treatment) from IxRS data will be used for the primary analysis. For the stratification factor of MSKCC prognostic group from IxRS, some subjects with MSKCC Prognostic Score 2 were misclassified to intermediate risk on IRT system which should have been classified to poor risk per protocol. The poor risk group will be pooled with the intermediate risk group in the relevant stratified analyses based on IxRS data, the favorable risk group will remain intact.

Sensitivity analyses may be performed using the stratification factors from CRF data in clinical database.

Exploratory analyses for the primary efficacy endpoint ORR_{24w} and secondary efficacy endpoints of ORR and PFS based on IIR assessments will also be performed (refer to [Section](#)

5.8.1).

5.4.1 Primary Efficacy Analyses

The primary efficacy endpoint ORR_{24W} is defined as the proportion of subjects with BOR of CR or PR as of the Week 24 (after randomization) timepoint based on investigator assessments, during treatment or within 28 days after the last dose date but on or prior to the start of new anticancer therapy. Subjects with responses achieved after the start of new anticancer therapy or after 28 days from the last dose date will not be considered as responders.

The primary analysis of ORR_{24W} will be based on a non-inferiority test. The study hypothesis is that the ORR_{24W} for lenvatinib 14 mg QD in combination with everolimus 5 mg is non-inferior to the ORR_{24W} for lenvatinib 18 mg QD in combination with everolimus 5 mg in subjects with renal cell carcinoma following one prior VEGF-targeted treatment.

For this study, the non-inferiority of lenvatinib 14 mg QD in combination with everolimus 5 mg relative to lenvatinib 18 mg QD in combination with everolimus 5 mg is defined using 70% retention of the treatment effect of lenvatinib 18 mg QD in combination with everolimus vs. everolimus, which translated to the estimated odds ratio =0.76 for the non-inferiority margin following the approach of [Rothmann et al. \(2003\)](#).

The non-inferiority hypothesis for ORR_{24W} with the non-inferiority margin of odds ratio =0.76 for the final analysis can be stated as follows:

H_0 : Odds ratio of $ORR_{24W-14mg}$ vs $ORR_{24W-18mg} \leq 0.76$

H_a : Odds ratio of $ORR_{24W-14mg}$ vs $ORR_{24W-18mg} > 0.76$ (non-inferiority)

The primary analysis of ORR_{24W} will be performed on the Per-Protocol Analysis Set 1. The point estimate of ORR_{24W} with the corresponding 95% CI for each treatment arm will be summarized. The odds ratio of ORR_{24W} (lenvatinib 14 mg over lenvatinib 18 mg) along with the 90% CI will be calculated using the CMH method stratified by MSKCC prognostic group and prior PD-1/PD-L1 treatment. Non-inferiority in ORR_{24W} will be claimed if the O'Brien-Fleming efficacy boundary is crossed. If the 1-sided P value is ≤ 0.045 at the final analysis, non-inferiority in ORR_{24W} will be claimed (interim analysis is specified in [Section 6](#)). The boundary P value ≤ 0.045 for the final analysis is based on the plan that the two interim analyses will take place when the total number of 150 subjects and 200 subjects in the Per-Protocol Analysis Set 1 have completed 24 weeks of follow-up or discontinued early.

The treatment difference in ORR_{24W} between lenvatinib 14 mg and lenvatinib 18 mg will also be estimated along with 90% CIs based on the asymptotic normal approximation.

If non-inferiority in ORR_{24W} is claimed, the superiority test at 2-sided $\alpha=0.05$ for the primary safety endpoint will be performed. The details are specified in Primary Safety Endpoint [Section](#)

5.6.1.

Sensitivity analyses of ORR_{24W} based on Full Analysis Set and Per-Protocol Analysis Set 2 will be performed in a similar manner as described above.

To explore homogeneity of treatment effect across centers/regions, a sensitivity analysis of ORR_{24W} using logistic regression model with center/region along with stratification factors as covariates will be conducted to adjust center/region effect.

Sensitivity analyses of ORR_{24W} based on the stratification factors from CRF data in clinical database will also be performed on Per-Protocol Analysis Set 1, Full Analysis Set and Per-Protocol Analysis Set 2.

For this study, for subjects in the lenvatinib 14 mg QD with everolimus 5 mg arm, lenvatinib dose should be escalated to 18 mg QD (with everolimus 5 mg) as long as there are no intolerable Grade 2 or any \geq Grade 3 TEAEs that require dose reductions in the first 28-day cycle. To evaluate any potential impact due to failing to up-titrate the doses for eligible subjects in the lenvatinib 14 mg QD with everolimus 5 mg arm, another sensitivity analysis may be performed on Per-Protocol Analysis Set 1 to exclude those subjects who should have been up-titrated by protocol but were actually not up-titrated by investigators, if the number of such cases in the lenvatinib 14 mg QD with everolimus 5 mg arm is deemed high (eg, $\geq 10\%$).

An analysis of ORR_{24W} based on the data prior to when the protocol was amended to open-label (from double-blinded) (ie, treatment assignments were unblinded to investigator sites on 14 July 2018) will be performed on Per-Protocol Analysis Set 1 and Per-Protocol Analysis Set 2 to check for consistency of study results before and after the protocol became un-blinded.

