9.7.1.6 Efficacy Analyses

9.7.1.6.1 PRIMARY EFFICACY ANALYSIS

Primary analysis of ORR_{24W} will be based on a non-inferiority test. There will be two interim analyses and the primary analysis. The two interim analyses will be performed using only Per-Protocol Analysis Set 1. The primary analysis will be performed using the Per-Protocol Analysis Set 1 as the primary analysis set and will also be performed using Per-Protocol Analysis Set 2 and the Full Analysis Set as secondary analysis sets. At each interim analysis and primary analysis, the point estimate of ORR_{24W} for each treatment group (18 mg and 14 mg) will be summarized with the corresponding 95% confidence interval (CI). The odds ratio of ORR_{24W} (14 mg vs 18 mg) along with the 90% CI will be calculated using the Cochran-Mantel-Haenszel (CMH) method stratified by MSKCC prognostic groups and prior PD-1/PD-L1 treatment. Non-inferiority in ORR_{24W} will be claimed if the O'Brien-Fleming efficacy boundary is crossed at either interim analysis or primary analysis based on the results from the Per-Protocol Analysis Set 1. If the 1-sided P -value is ≤ 0.005 at the first interim analysis, or ≤ 0.014 at the second interim analysis, or ≤ 0.045 at the primary analysis, non-inferiority in ORR_{24W} will be claimed. Futility will be claimed if the futility boundary is crossed. If the 1-sided P -value is ≥ 0.776 at the first interim analysis, or ≥ 0.207 at the second interim analysis, futility will be claimed. The treatment difference in ORR_{24W} for 14 mg vs 18 mg will also be estimated along with 90% CIs based on the asymptotic normal approximation.

At each interim analysis and at the primary analysis, if the noninferiority boundary of the primary efficacy endpoint is crossed, the analysis of the primary safety analysis will be performed for Per-Protocol Safety Analysis Set. The primary safety endpoint is the proportion of subjects with intolerable Grade 2 or any \geq Grade 3 TEAEs within 24 weeks after randomization (as of the Week-24 time point). Frequency (number and percentage) will be summarized for intolerable Grade 2 or any \geq Grade 3 TEAEs within 24 weeks after randomization by treatment. The proportions will be tested using the CMH test (2-sided $\alpha=0.05$), stratified by MSKCC prognostic groups and prior PD-1/PD-L1 treatment. The proportions of the primary safety endpoint will also be summarized for Safety Analysis Set for descriptive purpose.

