5.3.3 Multiple Comparisons/Multiplicity

There will be two interim analyses and one final analysis for the non-inferiority test on the primary efficacy endpoint ORR_{24W}. O'Brien-Fleming efficacy boundary is used to control the overall Type I error rate at the nominal level ($\alpha=0.05$ one-sided). Specifically, if the 1-sided P value is ≤ 0.005 at the first interim analysis, or ≤ 0.014 at the second interim analysis, or ≤ 0.045 at the final analysis, non-inferiority in ORR_{24W} will be claimed.

A non-binding futility will be also carried out at each interim analysis. If the 1-sided P value is ≥ 0.776 at the first interim analysis, or ≥ 0.207 at the second interim analysis, futility will be claimed.

These stopping boundaries are based on the plan that the two interim analyses will take place when the total number of 150 subjects and 200 subjects in the Per-protocol Analysis Set 1 have completed 24 weeks of follow-up or discontinued early.

Superiority on the primary safety endpoint will be tested at 2-sided $\alpha=0.05$ only if the non-inferiority on the primary efficacy endpoint ORR_{24W} is claimed.

All secondary efficacy endpoints will be analyzed descriptively, no formal statistical hypothesis tests will be performed on the secondary efficacy endpoints.

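### At the final analysis the primary odds ratio is reported with a 90% CI but tested at 1-sided 0.045, so the interval can exclude 0.76 when non-inferiority is not claimed (minor)

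*SAP*

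**What the plan says.** SAP 5.4.1 states the hypothesis on the odds-ratio scale, "with the non-inferiority margin of odds ratio =0.76 for the final analysis". It then asks for the odds ratio of 14 mg over 18 mg, "along with the 90% CI will be calculated using the CMH method stratified by MSKCC prognostic group and prior PD-1/PD-L1 treatment".

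The claim itself rests on a P value. Non-inferiority "will be claimed if the O'Brien-Fleming efficacy boundary is crossed", which at the final analysis means a 1-sided P of 0.045 or less. The SAP adds that this level "for the final analysis is based on the plan that the two interim analyses will take place" at 150 and 200 subjects. SAP 5.3.3 says that the O'Brien-Fleming "efficacy boundary is used to control the overall Type I error rate at the nominal level", namely one-sided 0.05 over the three looks.

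Protocol 9.7.1.6.1 and the Protocol synopsis contain the same pair: an odds ratio "along with the 90% CI will be calculated using the Cochran-Mantel-Haenszel (CMH) method stratified by MSKCC prognostic groups and prior PD-1/PD-L1 treatment", and the 0.045 level for the primary analysis. Both documents also give a 90% CI for the difference in ORR24W.

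Neither document provides an interval matched to the boundary. Neither labels the primary 90% interval as descriptive, or says how to read one that excludes 0.76 when the boundary is not crossed.

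**The concern.** Readers of a non-inferiority trial usually check whether the lower confidence limit clears the margin. Here the reported interval uses 5% in the lower tail and the decision uses 4.5%, so the two can disagree, and the plan gives no rule for that case.

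The point is small, but it sits on the primary endpoint. The non-inferiority claim opens the test of the primary safety endpoint (SAP 5.3.3 and 5.6.1), so a disagreement would invite dispute over whether that test was allowed. The dosing conclusion is left to clinical judgment over all the data, and this interval will be among the figures considered. The sensitivity analyses in the Full Analysis Set and Per-Protocol Analysis Set 2 are to be done in a similar way and inherit the mismatch.

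**Working it through.** **Inputs.** Margin 0.76; final 1-sided level 0.045; response rates 37% (18 mg) and 45% (14 mg); 153 subjects per arm; looks at 150, 200 and 306 subjects (SAP 4). Odds-ratio boundaries 1.788, 1.436 and 1.128 (SAP 13.1, Protocol Appendix 13).

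**1. Standard error at the design rates.** SE = √{[1/(0.37 × 0.63) + 1/(0.45 × 0.55)] / 153} = √(8.330/153) = 0.2333.

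**2. Reproducing the plan's boundaries.** O'Brien-Fleming-type spending of one-sided 0.05 at information 150/306, 200/306 and 1 gives boundary P values of 0.0051, 0.0138 and 0.0451 (z = 2.568, 2.203, 1.694). The final odds-ratio boundary is exp(ln 0.76 + 1.694 × 0.2333) = exp(−0.2744 + 0.3953) = 1.128. The same formula with SE 0.333 and 0.289 gives 1.788 and 1.436. All three match the documents.

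**3. Where the 90% lower limit reaches the margin.** exp(ln 0.76 + 1.645 × 0.2333) = exp(0.1094) = 1.116. The interval and the decision therefore disagree for an observed odds ratio of about 1.116 to 1.128 (1.129 if the rounded level 0.045, z = 1.695, is used).

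**4. Probability of disagreement at the final look.** Take Z as normal with mean ln(OR/0.76)/0.2333 and variance 1. Disagreement means 1.645 < Z < 1.695.

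| True OR | Mean of Z | Probability |
|---|---|---|
| 0.76 | 0 | 0.0500 − 0.0450 = 0.5% |
| 1.0 | 1.176 | Φ(0.519) − Φ(0.469) = 1.8% |
| 1.393 (45% vs 37%) | 2.597 | Φ(−0.902) − Φ(−0.952) = 1.3% |

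The width of the zone is 0.0505 on the Z scale, so no true odds ratio can give more than 0.0505 × 0.399 = 2.0%. These probabilities ignore stopping at the interims. At the planning rates, a simulation conditional on reaching the final look gives about 2.3%.

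**5. Example.** 70/153 on 14 mg, 66/153 on 18 mg.
- OR = (70 × 87)/(66 × 83) = 1.112; ln OR = 0.1059.
- SE = √(1/70 + 1/83 + 1/66 + 1/87) = 0.2302.
- Z = (0.1059 + 0.2744)/0.2302 = 1.652; 1-sided P = 0.0492, so there is no claim.
- 90% lower limit = exp(0.1059 − 1.645 × 0.2302) = 0.761, above the margin.
- 91% lower limit = exp(0.1059 − 1.695 × 0.2302) = 0.753, below the margin and in agreement with the test.

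The odds ratio is slightly under 1.116 because the standard error at these counts is below the design value of 0.2333. With 66 responders on 18 mg, 70 is the only 14 mg count that produces the conflict. A count of 69 fails on both criteria (OR 1.083, 90% lower limit 0.741). A count of 71 passes on both (P = 0.039, 91% lower limit 0.773).

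**The case against.** The strongest reply is that the decision never uses the interval. Both documents claim non-inferiority only on the P-value boundary and also tabulate the equivalent odds ratios. Neither says that a lower limit above 0.76 means non-inferiority. This is right, and it limits the point to reporting.

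A reader might infer that the type I error is inflated. Reading the final 90% limit as the test would give an overall 1-sided error of about 0.0545, and reading it at all three looks about 0.092. The documents contain no such rule. Under the rule they do contain, the error stays at 0.05.

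A reader might also point to the much wider conflict zones at the interims, with observed odds ratios of 1.315 to 1.788 and 1.222 to 1.436. SAP 6 records that both interim DMC meetings took place in March and June 2019 and that the study continued. SAP version 2.0 is dated April 2020, so those zones cannot now be acted on. It is also not explicit that a 90% interval was planned at each look. In Protocol 9.7.1.6.1 the words "At each interim analysis and primary analysis, the point estimate of" ORR24W govern the per-arm estimates, and the odds-ratio sentence follows without repeating them. The SAP sentence concerns the final analysis.

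Finally, 90% is the level used for the other between-arm contrasts (the ORR odds ratio and the hazard ratios), and it corresponds to the overall one-sided alpha. As a convention that is defensible. But SAP 5.3.3 calls the secondary efficacy analyses descriptive and says no such thing of the primary interval, which is on the same scale as the margin.

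**Conclusion.** The point holds as a minor reporting inconsistency at the final analysis. The interval level (1-sided 0.05) is looser than the decision level (1-sided 0.045), and nothing in the plan tells the reader which governs when they differ. The conflict zone is an observed odds ratio of about 1.116 to 1.128. Its probability is about 0.5% to 1.8% at the three true odds ratios examined and at most 2.0% before conditioning on the interim results. The formal rule, its alpha, the sample size and the power are not in question.

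The figures assume the design response rates, equal arms of 153 and an unstratified Wald standard error. The planned stratified CMH interval will shift the zone slightly. That 90% and 91% intervals correspond to different tests does not depend on these assumptions.

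**What to change.** In SAP 5.4.1, report the stratified odds ratio at the final analysis with a two-sided interval of level 1 − 2 × 0.045 = 91.0%. State that non-inferiority corresponds to its lower limit exceeding 0.76. The P value and the interval should come from the same stratified estimate and standard error, otherwise they can still disagree near the boundary. If the final level is recalculated because the interim timing differed from plan, the interval level should follow it.

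If a 90% interval is kept, including the one for the difference in ORR24W, label it as descriptive and not for comparison with the margin. SAP Table 1 restates the margin on the difference scale, so that interval invites the same comparison. Use the same wording in Protocol 9.7.1.6.1 and the synopsis.

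The cost is a few sentences, a changed level in the table shell and a slightly wider interval: in the example the lower limit moves from 0.761 to 0.753. No data, boundary, sample size or error rate changes.

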5.4.2 Secondary Efficacy Analyses

The secondary efficacy endpoints include PFS, ORR, OS, PFS2. The analysis of secondary efficacy endpoints will be performed descriptively based on the Per-Protocol Analysis Set 1 as the primary analysis set, Per-Protocol Analysis Set 2 and Full Analysis Set as the secondary analysis sets.

5.4.2.1 Progression-free Survival

DEFINITION

PFS is defined as the time from the date of randomization to the date of first documentation of disease progression based on investigator assessments or date of death, whichever occurs first.

Determination of the date of PFS event or censoring is summarized in Table 5 below.

Table 5 PFS Event and Censoring Rules

No.	Situation	Date of Progression or Censoring	Outcome
1	No baseline or postbaseline adequate tumor assessments	Date of randomization	Censored
2	Progression documented between scheduled visits, on or prior to new anticancer therapy [#] and within 28 days after the last dose of study treatment	Date of first radiologic PD assessment	PFS Event
3	No progression at the time of data cutoff	Date of last adequate radiologic assessment on or prior to data cutoff	Censored
4	New anticancer therapy started	Date of last adequate radiologic assessment on or prior to the start of new anticancer therapy	Censored
5	Death before first PD assessment, on or prior to start of new anticancer therapy [#] and within 28 days after the last dose of study treatment	Date of death	PFS Event
6	Death between adequate assessment ^{#,*}	Date of death	PFS Event
7	Death or progression after more than one missed visit/tumor assessment ^{**}	Date of last adequate radiologic assessment before missed tumor assessments	Censored
8	Death or progression after 28 days from the last dose of study treatment	Date of last adequate radiologic assessment before the date of last dose of study treatment + 28 days	Censored
9	No progression and treatment discontinuation for reasons other than PD	Date of last adequate radiologic assessment before treatment discontinuation (ie, within last dose date + 28 days)	Censored

Note:

If documented PD and/or death occurs after the last dose, it is counted as a PFS event as long as the PD and/or the death occurs within 28 days since the date of the last dose of study treatment and provided that it does not violate other censoring rules (eg, start of new anticancer therapy before the PD or death). Otherwise the subject will be censored on the date of the last tumor assessment before the date of last dose of the study treatment.

* Adequate tumor assessment is radiologic assessment of CR, PR, SD, non-CR/non-PD or PD as determined by investigators at regular interval as defined in the protocol. Any tumor assessments after new anticancer therapy starts or after 28 days from the last dose date will not be considered in the definition of PFS.

** More than one missed visit/adequate tumor assessment is defined as having the duration between two consecutive tumor assessments or the duration between the last adequate tumor assessment and death/PD being longer than (>) 118 days (the visit schedule for tumor assessment is during every 8th week for this study).

The priority of the censoring rules is described as follows:

1. If the subject had PD or death, the following sequence will be applied:

- If a subject did not have baseline or postbaseline adequate tumor assessments (No. 1), the subject will be censored at the date of randomization. However, if the subject died within 118 days after randomization and did not receive any new anticancer therapy, it will be counted as a PFS event at the date of death. If a subject had new anticancer therapy before PD or death (No. 4), the subject will be censored at the date of the last adequate tumor assessment on or prior to the date of new anticancer therapy. If PD is reported after the date of the last dose + 28 days, the subject will be censored at the date of last tumor assessment before the date of last dose + 28 days (No. 8). If PD or death happened within 28 days after the last dose date, it will be considered as a PFS event.
 - If a subject missed two or more tumor assessments before PD or death (No. 7), the subject will be censored at the date of the last adequate tumor assessment before the missed tumor assessments. Note that if a subject is censored by both of this criterion and start of new anticancer therapy criterion, the earliest censoring date will be used.
 - Otherwise, if a subject had PFS event (No. 2, No. 5 or No. 6), the earliest event date will be used.
2. If a subject did not have PD or death, the censoring date will be the earliest censoring date if the subject met multiple censoring criteria (No. 1, No. 3, No. 4, No. 7).

ANALYSIS METHOD

The analysis of PFS will be performed based on the Per-Protocol Analysis Set 1 as the primary analysis set. The median PFS and the PFS rates at 6, 12, 18 months, and so on (depending on data adequacy) will be estimated using the Kaplan–Meier method and presented with 2-sided 95% CIs. The hazard ratio of lenvatinib 14 mg over lenvatinib 18 mg and the corresponding 90% CIs will be estimated using the Cox regression model with Efron's method for ties, stratified by MSKCC prognostic group and prior PD-1/PD-L1 treatment. The Kaplan-Meier curve of PFS will also be plotted over time for each treatment arm.

Sensitivity analyses of PFS based on the Per-Protocol Analysis Set 2 and Full Analysis Set will be performed in a similar manner as described above.

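### The Note to SAP Table 5 gives a different PFS censoring date from row No. 8 for events more than 28 days after last dose, and no planned analysis tests that cut-off

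*SAP*

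**What the plan says.** All of the conflicting text is in SAP 5.4.2.1.

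- **Table 5 No. 8.** The situation is "Death or progression after 28 days from the last dose of study treatment" and the censoring date is "Date of last adequate radiologic assessment before the date of last dose of study treatment + 28 days".
- **Note under Table 5.** Progression or death after last dose is an event if it falls within 28 days and breaks no other censoring rule. The Note then ends: "Otherwise the subject will be censored on the date of the last tumor assessment before the date of last dose of the study treatment". The 28 days are missing from that date.
- **Priority text.** "If PD is reported after the date of the last dose + 28 days, the subject will be censored" at the No. 8 date, and that row is cited. The sentence names progression only. An exception makes early death an event for a subject without adequate assessments: "if the subject died within 118 days after randomization and did not receive any new anticancer therapy".
- **No. 9 and the footnote on adequate assessments.** Both use the 28-day window. The footnote says that scans "after 28 days from the last dose date will not be considered in the definition of PFS".
- **Planned sensitivity analyses.** "Sensitivity analyses of PFS based on the Per-Protocol Analysis Set 2 and Full Analysis Set will be performed in a similar manner".

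Scans do not stop with study drug. Protocol 9.3.3, protocol Table 6 footnote n, and SAP 3.2 and 8.1 require them every 8 weeks after discontinuation without progression, until progression or new therapy; the two protocol passages also stop them at data cutoff. Protocol 9.7.1.1.2 leaves PFS censoring to the SAP.

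**The concern.** There are two separate points.

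**Two dates.** No. 8 and the Note describe the same subject and differ by the 28-day window. Scans can fall inside that window: a scheduled scan may land there, and the Off-Treatment scan in protocol Table 6 footnote n is meant for that period. Two programmers working from the SAP could assign different dates. The programming rules are in separate documents (SAP 9) and may settle it, but the SAP should not contradict itself.

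**Untested cut-off.** Progression and death after day 28 are set aside even where they were documented. If prognosis changes once study drug stops, this censoring is informative. If 14 mg also leads to fewer toxicity stops, its effect would differ between arms. The PFS sensitivity analyses change the analysis set and nothing else. PFS by independent review uses the same definition (SAP 5.8.1), the optional CRF-strata analyses change only the strata (SAP 5.4), and the prior PD-1/PD-L1 analysis is a subgroup (SAP 5.8.2).

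What is at stake is a descriptive estimate. SAP version 2.0 added a PFS hazard ratio, and protocol 9.7.1.6.1 says the decision on 14 mg rests on the totality of the safety and efficacy data.

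**Working it through.** The plan has no figure of its own to reproduce here. The check is a comparison of dates, followed by simulation.

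**Date example** (assumed dates, scans every 56 days). Last dose is on day 100, so last dose + 28 is day 128. Scans are on days 56, 112 and 168.

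- Progression at the day-168 scan, 68 days after last dose: No. 8 and the priority text give day 112, the Note day 56. The priority text settles this case.
- Death on day 150, 50 days after last dose, no progression seen: No. 8 gives day 112, the Note day 56. Nothing settles this case.
- New therapy on day 120 and death on day 125: No. 4 gives day 112, the last scan on or before new therapy. The Note's last sentence also applies and gives day 56.

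**How often the dates differ, by last-dose day.** Let u be the days from the previous scheduled scan to last dose, u = 1 to 56.

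- Scheduled scans only: the next scan falls before last dose + 28 when 56 < u + 28, so u > 28. That is 28/56 = 50% of last-dose days, each with a 56-day gap.
- Off-Treatment scan on day 14, done if more than 28 days have passed since the last scan: u + 14 > 28 adds u = 15 to 28, which is 14 more days. (28 + 14)/56 = 75%, with gaps of 29 to 56 days.

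These are shares of last-dose days, not of subjects with late progression. Progression seen on a scan inside the window is an event, so subjects with late progression more often had no scan there. In simulation the dates differ for 39–45% of late-progression subjects with scheduled scans only, and for 67–72% with an Off-Treatment scan.

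**Simulation set-up.** Every input below is an assumption unless a source is given.

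- On-treatment median PFS of 8, 12 or 16 months, equal in both arms.
- Toxicity stops of 23.5% at 18 mg (Study 205, protocol 7.1) and 12%, 18% or 23.5% at 14 mg.
- 0% or 40% of stoppers start new therapy before progression.
- Hazard after stopping multiplied by 1, 2 or 3.
- Follow-up uniform over 6–30 months.
- Exponential times, progression dated at the next scan, Cox model with Efron ties.

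That gives 3 × 3 × 2 × 3 = 54 scenarios, each run under three scan schedules. Late deaths were not modelled.

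**Note date instead of No. 8 date.** Between 4 and 32 of 306 subjects get a different date. The hazard ratio moves by at most 0.009 and the 18-mg 12-month PFS rate by at most 0.6 points. The Kaplan-Meier median does not move.

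**28-day cut-off compared with counting all progression before new therapy.** The cut-off drops 9–48 documented events among 306 subjects.

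| Hazard after stopping | 18-mg 12-month rate | 18-mg median | HR shift, 14-mg stops 12% / 18% / 23.5% |
|---|---|---|---|
| unchanged | ≤0.8 points | unchanged | ≤0.006 in all |
| ×2 | +1.1 to 3.4 points | +0 to 0.9 months | 0.026–0.049 / 0.012–0.026 / ≤0.003 |
| ×3 | +1.8 to 5.2 points | +0 to 1.8 months | 0.035–0.072 / 0.017–0.036 / ≤0.004 |

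Where 14 mg has fewer stops, the hazard ratio moves toward 1.

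**Chance error.** The 90% CI factor is exp(1.645 × 2/√d), where d is the number of events. For d = 138 it is exp(3.29/11.75) = 1.32; for d = 239 it is exp(3.29/15.46) = 1.24. Every shift in the table is smaller than this.

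**The case against.** The strongest reply is that the SAP already answers most of the first point. The priority text gives the No. 8 date for late progression, and No. 9 and the footnote on adequate assessments use the same window. That stands. A reader might infer that every subject with a late event has an undetermined date, and the documents do not support that. What stays open is late death without earlier progression. No. 8 does name death, but so does the Note, and no text says that the Note yields.

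A reader might also take 50% or 75% as the share of affected subjects. Those figures describe last-dose days; the shares among late-progression subjects are those from the simulation. The simulated effects cover late progression only, so the one case left open has no estimate.

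On the second point, the reply is that the cut-off is a design choice the protocol allows, and that a sizeable effect needs a doubled or tripled hazard with no source in the documents. Both statements are correct. Nor are later events lost from reporting: OS counts all deaths on study (SAP 5.4.2.3), PFS2 counts any death or progression on the next line (SAP 5.4.2.4), and neither has a 28-day limit. Discontinuations and their reasons are also summarised (SAP 5.2.2, 5.6.3.6). None of these is a PFS analysis under a different cut-off, so the gap remains, but it is a small one.

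**Conclusion.** Both points hold in limited form. The last sentence of the Note contradicts No. 8 and should be corrected. It is the outlier for late progression, it leaves late death undecided, and it also conflicts with No. 4 and can conflict with No. 7. The numerical effect for late progression is negligible: at most 0.009 on the hazard ratio and 0.6 points on the 12-month rate.

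The 28-day cut-off is not an error, and the documents do not support a claim that it biases PFS. With an unchanged hazard after stopping there is no material bias. If the hazard doubles or triples, which is purely an assumption, the 18-mg 12-month rate is overstated by about 1 to 5 points and the hazard ratio shifts by up to about 0.07, below chance error. The gap is only that no prespecified PFS analysis would show whether this occurs.

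A reader might infer a threat to the trial's main conclusions. PFS is secondary and descriptive with no hypothesis test (SAP 5.3.3, 5.4.2), so no confirmatory claim depends on it. Severity is low.

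**What to change.** **1. Make the text consistent.** Replace the last sentence of the Note with a pointer: a subject who does not qualify as an event takes the date from whichever of No. 4, No. 7 or No. 8 applies, in the stated priority order. For progression or death more than 28 days after last dose, that is the last adequate assessment on or before last dose + 28 days. Use the same on-or-before wording in No. 8 and No. 9, so that a scan on day 28 itself is treated as the footnote on adequate assessments treats it. In the priority sentence for No. 8, name death as well as progression, and keep the 118-day early-death exception.

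A single last-dose + 28-day date for everyone in the Note would not work. Take a scan on day 56, last dose on day 170 and progression on day 180, so the gap is 124 days and exceeds 118. No. 7 gives day 56, while the single date would be day 180, the progression scan itself.

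**2. Add one prespecified sensitivity analysis.** Analyse investigator-assessed PFS in Per-Protocol Analysis Set 1, counting every documented progression or death before new anticancer therapy whatever the last-dose date. Keep No. 4 and No. 7. For that run only, lift the 28-day limits in Nos. 2, 5, 8 and 9, the Note, the footnote on adequate assessments and the priority text. The main rule is unchanged.

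**Cost.** A few words, and one extra run on scans and deaths already collected until progression, new therapy or data cutoff. The added run mixes time on and off study drug, which is why it should remain a sensitivity analysis.
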